7.1.4 Continuation Phase (fulvestrant +/- everolimus)

Patients with no evidence of disease progression after 12 cycles of treatment (Induction Phase) will be unblinded and proceed to the Continuation Phase. Patients in the Continuation Phase should continue to receive fulvestrant alone (if originally randomized to placebo) **or** in combination with everolimus (if originally randomized to everolimus) at the same dose and schedule until disease progression is documented or unacceptable toxicity. Once progression is documented, patients will move into Follow-Up Off Therapy.

One cycle in the Continuation Phase is equal to 28 days. Day 1 of the Continuation Phase should start 28 days (D29) after the last dose of fulvestrant was given during Cycle 12 in the Induction Phase.

All adverse events that are related to fulvestrant and/or everolimus will be followed for 30 days after the last dose of study therapy (fulvestrant and/or everolimus) until \leq grade 1 or if the grade is >1 , the event must be permanent and stable.

- CBC and chemistry may be used to monitor any ongoing toxicities, but are not required for patients that receive fulvestrant alone.
- Patients who continue fulvestrant in combination with everolimus should periodically have CBC, chemistries, fasting glucose, fasting serum lipids, HBV DNA, and HCV RNA-PCR per labeling guidelines.
- Study Drug Compliance (Pill Diary) for those patients who receive everolimus in the Continuation Phase.

After the Continuation Phase, serious adverse events >30 days after last dose of fulvestrant and/or everolimus are not reported unless the event may be related to everolimus.

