9.1 Primary Efficacy Endpoint

The primary efficacy endpoint is progression-free survival (PFS). PFS is defined as the time from randomization to documented disease progression or death. Based on results from the CONFIRM trial, median PFS among patients with AI-resistant disease on fulvestrant alone is 5.4 months. AI resistant disease is defined as: patients who have either relapsed while receiving adjuvant therapy with an aromatase inhibitor (anastrozole, letrozole, or exemestane) or have progressive disease while receiving an aromatase inhibitor for metastatic disease. (Patients previously treated with two or more prior cycles of fulvestrant are not eligible. Patients who have received one prior cycle (day 1 and day 15) of fulvestrant within 28 days of randomization are eligible so long as they meet other eligibility criteria). Randomization will be 1:1, stratified for balancing purposes using ECOG performance status (0 vs. 1), presence of measurable disease (yes vs. no), and prior chemotherapy (yes vs. no).

We hypothesize that the addition of everolimus to fulvestrant will result in an improvement in median PFS to 9.2 months. A one-sided stratified logrank test with a type I error rate of 10% will be used to evaluate whether the addition of everolimus shows promising improvement in PFS relative to fulvestrant alone. To have 90% power to detect the hypothesized improvement, enrollment of approximately 120 eligible patients (60 per arm) and full information of 98 events (deaths or progressions) are required. Allowing up to 10 patients to be ineligible or to not start study treatment, approximately 130 patients will need to be enrolled. With accrual of approximately 130 patients in 12 months, the required 98 events are expected to occur approximately 12 months after accrual is completed. Other endpoints that will be evaluated include clinical benefit rate (proportion stable or responding for at least 6 months), objective response rate (CR+PR), time to progression (TTP; defined as the time from randomization until progression of the disease), and overall survival (OS; defined as the time from randomization until death or censored at the date of last follow-up).

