9.2 Safety Analyses

A descriptive comparison of overall toxicity and of grade 3-4 toxicity in the combination arm and the fulvestrant arm will be provided. Assuming 65 patients are treated on each arm, the exact binomial 90% confidence interval on the rate of severe toxicities will be no wider than 22% (+/- 11%). The probabilities of observing a rare toxicity (true rate of 5%) will be 96% on each arm.

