## **7.8. Safety Analysis**

### **7.8.1. Adverse Events**

Adverse events (AEs) will be graded using CTC Version 4, coded using MedDRA dictionary version 16.0, and flagged as treatment emergent if start date of the adverse event is on or after Cycle 1 Day 1 dosing. For adverse events with partial start date (i.e., with only month and year are recorded), the following imputation rule will be applied: 15th of the month or first dose date, whichever comes later.

All AEs and treatment-related AEs will be summarized for all treated subjects by toxicity grade and by treatment arm.

AEs with relationship reported as 'Definite', 'probable' and 'possible' are considered study drug related. AEs with relationship reported 'not likely' and 'not related' are considered not study drug-related. AEs with missing relationship will be considered study drug related.

The following by subject data listings will be prepared: subjects with serious adverse events, subjects with Grade 5 adverse events, and subjects with second primary cancer.

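### Adverse-event tables pool blinded Induction with open-label Continuation, where laboratory monitoring and time on treatment differ by regimen, with no split by phase and no exposure adjustment

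*Protocol*

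**What the plan says.** Protocol 9.2 plans a between-arm safety comparison: "A descriptive comparison of overall toxicity and of grade 3-4 toxicity in the combination arm and the fulvestrant arm will be provided". SAP 7.8.1 carries it out as follows: "All AEs and treatment-related AEs will be summarized for all treated subjects by toxicity grade and by treatment arm". SAP Appendix 1 specifies tables 8 to 11 by arm and grade, with each patient entered once at worst grade. The treatment-emergent definition in SAP 6.1 and 7.8.1 has a start (first dose) but no end and no phase limit. The dosing table (SAP 7.5; Appendix 1, table 7) is split into Induction and Continuation; the AE tables are not.

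During Induction both arms follow one visit and laboratory schedule under blind (Protocol 7 and 7.1.2). Patients free of progression after 12 cycles are unblinded and enter Continuation. Under Protocol 7.1.4 and note k of the study table, CBC and chemistry may be used there to follow ongoing toxicity but "are not required for patients that receive fulvestrant alone". Patients still on everolimus should have CBC, chemistry, fasting glucose, fasting lipids and viral tests from time to time, as the label advises.

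**The concern.** Once Continuation events enter the same worst-grade count, three things differ between the regimens besides the drug effect.

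- **Laboratory ascertainment.** Fewer laboratory checks on fulvestrant alone can only lower detection there. Hyperglycemia, lipid changes and anemia are among the everolimus toxicities that Protocol 1.4.3.3 lists.
- **Blinding.** Under Protocol 10.1 the investigator judges whether a laboratory value is clinically significant, and whether an event is attributed to study drug. Attribution decides entry to the treatment-related tables. After cycle 12 both judgments are made knowing the arm.
- **Time at risk.** If everolimus prolongs PFS as hypothesized, its patients stay on treatment longer and accumulate more crude events even at an identical event rate.

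The first and third push the crude difference against everolimus. At stake is the interpretation of the toxicity comparison in the publication, not the primary endpoint.

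**Working it through.** **1. The plan's own figures.** Protocol 9.2 assumes 65 treated per arm. The chance of seeing at least one case of a 5% toxicity is 1 − 0.95^65 = 0.964 (stated 96%). The widest exact 90% interval for n = 65 is 0.216, at 33 cases (stated as no wider than 22%, or ±11 points). Both reproduce.

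The design inputs used below, from Protocol 9.1, are also coherent: "median PFS among patients with AI-resistant disease on fulvestrant alone is 5.4 months", the addition of everolimus "will result in an improvement in median PFS to 9.2 months", and "Randomization will be 1:1". The hazard ratio is 5.4/9.2 = 0.587. With "A one-sided stratified logrank test with a type I error rate of 10% will be used" and "To have 90% power to detect the hypothesized improvement", the Freedman formula gives (1.2816 + 1.2816)² × (1.587/0.413)² = 97 events, and Schoenfeld gives 93. The stated number is 98. None of these figures is in dispute.

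**2. Who reaches Continuation.** Twelve 28-day cycles are T = 336/30.4375 = 11.04 months. Assume exponential time on treatment with progression as the only exit.

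- Control: 2^(−11.04/5.4) = 0.242, or 15.8 of 65.
- Everolimus: 2^(−11.04/9.2) = 0.435, or 28.3 of 65.

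**3. Time in each phase.** With μ = ln 2/median, mean Induction time is (1 − e^(−μT))/μ. Mean Continuation time to follow-up F is (e^(−μT) − e^(−μF))/μ. Two horizons were used. The planned cut has 12 months of uniform accrual plus 12 more, so F runs from 12 to 24 months and results are averaged. The other is the protocol's three-year follow-up, F = 36.

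| Months per patient | Control | Everolimus |
|---|---|---|
| Induction | 5.90 | 7.50 |
| Continuation, planned cut | 1.04 (15% of total) | 2.24 (23%) |
| Continuation, 36 months | 1.81 (23%) | 4.90 (40%) |

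**4. Effect on a crude AE percentage.** The documents give no rate for laboratory AEs, so assume a 12-month risk r of 5% to 40%, **the same in both arms**, with hazard λ = −ln(1 − r)/12. The probability of a first event in Induction is λ/(λ+μ) × (1 − e^(−(λ+μ)T)). Continuation adds e^(−(λ+μ)T) × λ/(λ+μ) × (1 − e^(−(λ+μ)(F−T))). The worst case sets control detection in Continuation to zero. Because the true hazards are equal, any difference is an artefact.

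Example, r = 20%: λ = 0.0186. Induction incidence is 0.128 on everolimus (μ = 0.0753) and 0.102 on control (μ = 0.1284), a difference of 2.6 points.

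Spurious everolimus-minus-control difference, in percentage points:

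| Horizon | r | Induction only | Pooled, equal labs | Pooled, no control labs | Lab part |
|---|---|---|---|---|---|
| Planned cut | 5% | 0.7 | 1.1 | 1.6 | 0.4 |
| | 10% | 1.3 | 2.2 | 3.0 | 0.8 |
| | 20% | 2.6 | 4.3 | 5.8 | 1.5 |
| | 40% | 5.1 | 7.9 | 10.3 | 2.4 |
| 36 months | 5% | 0.7 | 1.9 | 2.6 | 0.7 |
| | 10% | 1.3 | 3.6 | 4.9 | 1.4 |
| | 20% | 2.6 | 6.5 | 9.0 | 2.4 |
| | 40% | 5.1 | 10.7 | 14.5 | 3.7 |

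The lab part is the step from equal labs to no control labs, before rounding: 0.4 to 3.7 points. The exposure part added by pooling is the step from Induction only to pooled with equal labs: from 1.1 − 0.7 = 0.4 to 10.7 − 5.1 = 5.6 points. The effect of unblinded reporting and attribution cannot be sized from the documents.

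**The case against.** The case on the other side is substantial.

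- **The laboratory rule is softer than it may look.** A reader might infer that labs are mandatory on everolimus and absent in controls. Protocol 7.1.4 does not say that. On everolimus they are periodic with no fixed interval, and on fulvestrant alone they are optional. The rule also follows treatment received, not arm: patients who stop everolimus for toxicity continue on fulvestrant alone (Protocol 5.3.1, 5.5), which dilutes the contrast. This stands.
- **Safeguards limit the effect.** Everyone has CBC, chemistry, glucose and lipids at the end of Induction (Protocol 7.1.3). AE assessment continues in both arms. Under Protocol 10.1 a laboratory value is an AE only if it is symptomatic, clinically significant or treated, although SAP 6.1 omits that limit. A missed value matters only if it would be a first event or a new worst grade after about 11 months. This stands.
- **There may be little to miss.** In the exemestane trial described in Protocol 1.4.3.4, control-arm grade 3 or 4 anemia and hyperglycemia were each below 1%. Protocol 8.2.3 lists leukopenia on fulvestrant at below 1% and no glucose or lipid events. For severe events this points to the low end of the range or below it. It says less about all-grade tables.
- **The lab part is small** beside the stated ±11 points. That is true, but an interval describes sampling error and does not cover a shift in one direction.
- **The comparison is descriptive.** No test or decision rule depends on it. This stands and limits the importance of the point.
- **The table templates are a separate document.** They might contain a split by phase. That cannot be excluded, but the SAP text that governs them provides none.

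**Conclusion.** The point holds in a limited form. As written, the AE tables combine a blinded phase with equal monitoring and an open-label phase in which monitoring and time at risk differ by regimen. A reader might go further and conclude that the toxicity comparison is biased against everolimus overall. The documents do not support that. The laboratory mechanism touches only laboratory-detected events after cycle 12, in about 16 control patients. Its maximum is 0.4 to 2.4 points at the planned cut and 0.7 to 3.7 points at 36 months. Over most of the range, the exposure effect of pooling crude percentages is as large or larger (0.4 to 2.8 points at the planned cut, 1.2 to 5.6 at 36 months).

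These sizes rest on exponential times at the design medians, progression as the only exit, an assumed equal AE hazard, and zero control detection in Continuation for the upper bound. Stopping everolimus for toxicity would lower the share of everolimus patients treated in Continuation, so the phase imbalance is probably somewhat overstated. The change is worth making before database lock because it is cheap, but neither the primary analysis nor any formal test depends on it.

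**What to change.** In SAP 7.8.1 and Appendix 1:

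1. Present tables 8 to 11 for events starting in the Induction Phase, and name this the like-for-like between-arm comparison.
2. Tabulate Continuation-onset events separately by arm, noting that the phase is open-label and that laboratory monitoring depends on the regimen received.
3. Keep the pooled all-treatment tables alongside, so that late-onset toxicity stays visible.
4. Add exposure-adjusted rates (patients with a first event per patient-month at risk), overall and by phase. Restricting to Induction alone still leaves a 0.7 to 5.1 point exposure difference under the assumptions above.

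The cost is a phase flag on AE onset, extra tables and a definition of time at risk. SAP 7.5 already separates the phases for dosing. No data collection or patient monitoring changes. The drawback is that late-onset events do not appear in the Induction comparison and must be read from the second and pooled tables.

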7.1.4.1 Every 12 Weeks

- Tumor evaluation every 12 weeks, \pm 1 week (every 3 months) during the Continuation Phase until disease progression is documented.

7.1.5 Follow-Up Off-Therapy

All patients, including those who discontinue protocol therapy, will be followed for 3 years from the time of randomization. Patients that did not progress during the Induction or Continuation Phase will continue to have imaging scans completed every 3 months until documented progression. Patients will then be followed for survival. Initiation of any new systemic therapy will also be documented. Patients that have adverse events related to fulvestrant and/or everolimus/placebo will be followed for 30 days after the last dose of study therapy (fulvestrant and/or everolimus/placebo) until \leq grade 1 or if the grade is >1 , the event must be permanent and stable. Serious adverse events >30 days after last dose of fulvestrant and/or everolimus/placebo are not reported unless the event may be related to everolimus/placebo.

8 Drug Formulation and Procurement

8.1 Everolimus

8.1.1 Packaging and Labeling

Full instructions for investigator sites and investigational pharmacies will be available in separate protocol-specific documents. The supply of everolimus or placebo will be shipped directly to the local investigator. Drug ordering procedures will be provided in supplemental study materials.

8.1.1.1 How Supplied

Everolimus and an identically appearing placebo will be provided by Novartis. Everolimus is formulated as tablets for oral administration of 5 mg strength. Tablets are blister-packed under aluminum foil in units of 10 tablets per blister card, which should be opened only at the time of administration as drug is both hygroscopic and light-sensitive. Each tablet contains as inactive ingredients: butylhydroxytoluene/butylated hydroxytoluene (BHT), magnesium stearate, lactose monohydrate, hypromellose, crospovidone and lactose anhydrous.

Medication labels will comply with US legal requirements and be printed in English. They will supply no information about the patient. The storage conditions for study drug will be described on the medication label.

8.1.2 Storage Requirements/Stability

Everolimus should be stored at room temperature between 20°C to 25°C (68°F to 77°F).

All investigational products must be kept in a secure place under appropriate storage conditions. A description of the appropriate storage and shipment conditions is specified on the investigational product label and investigator brochure. The stored study drug supplies must be accessible to authorized staff only. The storage area must also have adequate control of temperature in order to maintain stability and potency of study drug supplies. The tablets should be stored in the original pack until use. For further information, investigators should refer to the current Investigators Brochure (IB).

8.1.3 Handling, Dispensing and Administration

8.1.3.1 Handling

No special precautions are necessary when handling intact tablets. Avoid contact with skin and eyes. Wash hands after use. The risk to health in normal handling of tablets is very low. Exposure to dust from crushed tablets may cause adverse health effects.

8.1.3.2 Dispensing

Drug should be dispensed in original packaging. If other packaging is required by institutional policy, this procedure will need to be approved by PrECOG, or their designee, prior to proceeding. The PrECOG Site Contact should be contacted for further

instruction. Investigational product records should be kept as per Section 8.1.5 and institutional policies.

8.1.3.3 Administration

Patients should be instructed to take their assigned, once-a-day oral dose of everolimus/placebo at the same time each morning.

- Everolimus/placebo dose may be taken with or without food.
- Patients should be instructed to swallow the capsules whole and not chew them.
- Vomited doses should not be replaced.
- If the patient forgets to take the medication and remembers by 10 PM, they may take the dose. Otherwise, skip that dose and begin as usual the next day.

In cases where tablets cannot be swallowed, the tablets should be disintegrated in water just prior to being taken. Approximately 30 mL (2 tablespoons) of water should be put into a glass. The tablets should then be added and the contents stirred gently (for a maximum of 7 minutes) until the tablets are disintegrated. The contents should then be drunk.

Patients should be given instructions on correct dosing based on study requirements and toxicity management (dose modifications). All changes to recommended dosing regimen/schedule should be documented in the patient record. Documentation of patient instructions for dosing changes should also be in source records.

Patients should be instructed to record the reason for any missed doses and report to the investigator at the next visit. If a dose is vomited, that dose should not be replaced, (and recorded as a vomited dose).

Compliance with therapy will be assessed at the beginning of each cycle. Patients will be given a diary (see Appendix F for an Example Patient Pill Diary) for recording of doses of study drug as provided by each study site. A copy of the patient diary will be provided to sites in study materials.

8.1.3.4 Special Instructions for Unblinding

Patients on study therapy and all site study staff will remain blinded as to the assignment of everolimus or placebo. Patients who have not had progressive disease and remain on study after 12 cycles are unblinded and continue fulvestrant alone (if originally randomized to placebo) **or** in combination with everolimus (if originally randomized to everolimus) at the same dose and schedule in the Continuation Phase. If an emergency situation arises and the patient must be unblinded during the Induction Phase (Cycles 1-12), the Medical Monitor for the study must be consulted.

Emergency Unblinding for Patients during the Induction Phase (within Cycles 1-12):

Unblinding is a serious action that should be restricted in order to limit potential study bias. The breaking of the blinding code in all cases will render the patient off-protocol.

The Medical Monitor for the study must be involved in the decision to unblind and must grant approval for unblinding any individual. Requests for unblinding will only be considered in the event of an emergency or severe adverse reaction where identification

of the medication is considered important for the welfare of the patient, and the rationale for unblinding is applicable to the situation. All patients should be provided emergency medical care by the treating physician and appropriate therapies for the medical emergency should be initiated prior to the request for unblinding.

For example, a Serious Adverse Event (SAE) possibly, probably or definitely related to the study drug occurs during the trial and the treatment of the SAE would be influenced by whether he/she received everolimus or placebo. Unblinding is typically not necessary if the medical management of the patient would not be materially altered by knowledge of the treatment assignment. In the event that *accidental* unblinding occurs, the Principal Investigator should report the occurrence promptly to the Medical Monitor and document the incident in the patient records. All unblinding will be recorded as a protocol deviation.

If a participant is in a life-threatening situation in which knowledge of the treatment is crucial to care AND the Medical Monitor cannot be reached immediately, the PM should be contacted to facilitate the unblinding process. A report including the unblinding details will be generated after the patient has been unblinded and will be sent to the site for documentation (refer to Study Reference Manual for Unblinding Process). Report information will include but is not limited to:

- ID number of the participant whose treatment assignment was unblinded
- Date of unblinding and reconciliation of study drug in site and patient records
- Reason for unblinding, including initial SAE report
- Person responsible for unblinding
- List of persons who are unblinded (e.g. study staff)

8.1.4 Side Effects

The most common adverse reactions (incidence $\geq 10\%$) reported for everolimus include stomatitis, rash, fatigue, asthenia, diarrhea, anorexia, nausea, mucosal inflammation, vomiting, cough, peripheral edema, infections, dry skin, epistaxis, pruritus, and dyspnea. The most commonly reported grade 3-4 adverse reactions (incidence $\geq 2\%$) reported for everolimus include infections, stomatitis, fatigue, and pneumonitis.

8.1.5 Investigational Product Records at Investigational Site(s)

Investigational product dispensing record/inventory logs and copies of signed packing lists must be maintained at the investigational site for everolimus. It is the responsibility of the Investigator to ensure that a current record of investigational product disposition is maintained at each study site where investigational product is stored and/or dispensed. Records must comply with applicable regulations and guidelines, and should include:

- Amount received and placed in storage area.
- Amount currently in storage area.
- Label ID number or batch number.
- Dates and initials of person responsible for each investigational product inventory entry/movement.

- Amount dispensed to and returned by each patient, including unique patient identifiers.
- Amount transferred to another area for dispensing or storage.
- Non-study disposition (e.g., wasted, broken).
- Amount returned to manufacturer, if applicable
- Amount destroyed at study site, if applicable

